Statistical Analysis Plan: For the primary outcome assessment, intention to treat principle will be applied in the analysis of this randomized placebo-controlled trial. For analysis of our primary outcome of arterial inflammation, we will compare the mean changes in arterial inflammation as assessed by FDG-PET measured as target to background ratio (TBR) of standardized uptake value in the group is randomized to teduglutide to the group that is randomized to placebo using independent samples t-test. Secondarily, we will also examine whether or not the mean of within group changes during the intervention period is zero using paired sample t-test. For secondary endpoints including change in markers of intestinal permeability, innate immune activation and microbial translocation, we will use the independent samples t-test to compare the means of the changes between the teduglutide group and the placebo group. In addition, longitudinal linear mixed effects modeling will be applied. The model will include random subject level intercept, fixed discrete time and group, and time \times group interaction term to characterize the within-group longitudinal means and to compare the between group difference in those longitudinal means. Effects of the potential confounders, (lipids, age, gender, smoking, diabetes mellitus, hypertension and other cardiovascular risk factors that may be different between the groups), will be adjusted by including them in the model as the covariates. We will utilize all available observations for this modeling even if there are some patients who have missing data at any time. If necessary, we will also perform Markov Chain Monte-Carlo (MCMC) based multiple imputation procedure.

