Sample Size Determination: With 30 patients in each group and up to 10% attrition (i.e. evaluable n=27/group), this trial can detect at least a between group difference of 0.2244 in the two within person TBR mean changes at a 5% significance level with 85% power by a two-sided independent samples t-test. This assumed that the standard deviation of the within subject TBR change is 0.27, which was estimated from our prior study at MGH study of similar patient population²⁸ of which the observed mean \pm (standard deviation) of the cross sectional TBR data was 2.24 (\pm 0.35) and the assumed pre- to post intervention longitudinal correlation was 0.7. This detectable effect size is close to 10% of the baseline mean 2.24, and we anticipate that the placebo group will show no change (or even increase its mean value). The effect size of 10% is of clinical significance as it is similar to the amount of decrease seen with statin treatment for 3 months⁵⁹, the most effective medical therapy we have to date for treatment of atherosclerotic disease and prevention of MI.

VII. Risks and Discomforts

Colonoscopy: Colonoscopy are generally safe procedures and complications are rare. Given the underlying HIV infection of the study participants, there is potential for the sequellae of the endoscopy complications outlined below to be more serious and more difficult to treat.

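### In the Aim 2 mixed model, adding baseline confounders as main-effect covariates leaves the between-arm difference in change effectively unadjusted

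*Combined protocol and SAP*

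**What the plan says.** The Statistical Analysis Plan paragraph for the Randomized Study of Teduglutide vs. Placebo (Aim 2) has two layers.

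- **Unadjusted tests.** The mean change in TBR in the teduglutide arm is compared "to the group that is randomized to placebo using independent samples t-test". The secondary markers are compared in the same way.
- **An additional mixed model.** "The model will include random subject level intercept, fixed discrete time and group", plus a time × group interaction. Potential confounders (lipids, age, gender, smoking, diabetes, hypertension, and other cardiovascular risk factors that might differ between arms) "will be adjusted by including them in the model as the covariates". All available observations are used, including those of participants with gaps.

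For Aim 2 the paragraph gives no covariate × time term, no ANCOVA and no adjustment for the baseline outcome. It does not say whether covariates are fixed at baseline, whether the mixed model covers TBR as well as the secondary markers, or which contrast will be reported as the adjusted effect. The multivariate regression described earlier in the statistics section belongs to the cross-sectional Aim 1A.

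**The concern.** Every Aim 2 endpoint is a change, so the treatment effect in the mixed model is the time × group term. That term is a within-person contrast. A time-fixed covariate entered as a main effect explains why one participant sits higher than another, but it cancels when a participant's baseline is subtracted from the later value. The stated adjustment therefore acts on the group term (the gap at baseline) and does not reach the contrast of interest.

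Two things are at stake. If smoking or age is unbalanced by chance and predicts change, the adjusted difference in change carries that imbalance in full. And the precision that prognostic covariates could give is not obtained. The open-ended part of the covariate list also allows covariates to be chosen after imbalance has been seen.

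**Working it through.** **Inputs from the plan (Aim 2, Sample Size Determination).** A "between group difference of 0.2244 in the two within person TBR mean changes" is detectable "at a 5% significance level with 85% power by a two-sided independent samples t-test"; "the standard deviation of the within subject TBR change is 0.27"; "the assumed pre- to post intervention longitudinal correlation was 0.7"; cross-sectional SD 0.35; 27 evaluable per arm. FDG-PET is done at Visit 4 and repeated in the month-6 final visits, so TBR has two time points. Lipids are drawn at Visit 1 and again at month 6.

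**Step 1: reproduce the plan's figure.** SD of change = 0.35 × √(2 × (1 − 0.7)) = 0.271. The t-test noncentrality is 0.2244 / (0.27 × √(2/27)) = 3.054. With 52 df, power is 85.0% and the detectable difference is 0.22437. The plan's figure holds.

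**Step 2: the algebra.** Write participant *i*'s outcome at visit *t* as

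y(i,t) = time(t) + group + time × group + β·x(i) + b(i) + e(i,t).

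The change is y(i,6) − y(i,0). Both β·x(i) and b(i) cancel. With complete data the estimated time × group term is therefore the same whatever β is. If the covariate also enters with time, a term δ·x(i) remains in the change and can be estimated and removed.

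**Step 3: simulation at the plan's variance.** 150 trials per scenario, 30 per arm, SD 0.35, correlation 0.7, true treatment effect 0. Assumed for illustration: one covariate with a 0.5 SD imbalance that shifts TBR change by 0.1 per SD, so the expected carry-over is 0.5 × 0.1 = 0.05. Mean time × group estimates:

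| Scenario | No covariate | Main effect | Covariate × time |
|---|---|---|---|
| Two visits, complete | 0.0448 | 0.0448 | 0.0019 |
| Four visits, complete | 0.0469 | 0.0469 | −0.0087 |
| Two visits, 10% missing the last | 0.0430 | 0.0433 | −0.0099 |
| Two visits, 20% missing the last | 0.0426 | 0.0431 | −0.0070 |

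- Complete data: the largest difference between the first two columns in any trial was about 3 × 10⁻¹⁵, with the same standard error.
- 10% missing: the term moved by 0.003 on average (at most 0.0145).
- 20% missing: it moved by 0.005 on average (at most 0.035).
- The carry-over of 0.0448 is 0.0448 / 0.2244 = 20% of the detectable difference.

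**Step 4: a time-varying covariate.** With an assumed 0.3 SD on-treatment shift in a re-measured covariate, entering its current value moved the term by 0.029 on average (mean −0.0271 to 0.0014). What it removed was the part of the treatment effect that ran through the covariate.

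**Step 5: how often imbalance arises.** The SE of a standardized arm difference is √(2/27) = 0.272, or √(2/30) = 0.258 with 30 per arm. A gap of 0.5 SD or more has probability about 7% or 5% per covariate. For at least one of six it is 1 − (1 − p)⁶, about 34% or 28%, if the six are independent (an assumption).

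**Step 6: precision available.** The share of the variance of change explained by the baseline outcome is (1 − 0.7)/2 = 0.15. The residual SD is 0.27 × √0.85 = 0.249, the noncentrality is 0.2244 / (0.249 × √(2/27)) = 3.31, and with 51 df power is 90%, against 85% unadjusted. If other covariates explained 10% to 20% (assumed; the documents give no figure), power would be about 88% to 92%.

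**The case against.** The strongest reply is that the text is under-specified rather than wrong, and that little depends on it. Several parts of this stand.

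- **A reader might infer that covariates cannot move the term at all.** The documents do not support that. The plan uses all available observations, allows for up to 10% attrition, and does not fix lipids at baseline. The invariance is exact only for time-fixed covariates and complete data. Still, movement from missing visits corrects nothing, and movement from re-measured lipids comes from conditioning on a post-randomization variable.
- **The contrast to be reported is not stated.** The model is also meant to compare longitudinal means between arms. The month-6 difference in level is group plus time × group, and main effects do move it. In one simulated two-visit trial (27 per arm, assumed 0.5 SD imbalance) it went from 0.118 to −0.014, while the interaction stayed at 0.065. So one cannot say that the report will necessarily present an unadjusted effect as adjusted. It would if the difference in change is what is reported.
- **A reader might infer that the trial's main result is biased or its power misstated.** It is not. Allocation is randomized, so the unadjusted difference in change is unbiased by design. The primary analysis is the t-test, and the sample size is built on that test.
- **The wording about differences between arms** may qualify only the other risk factors, since six covariates are already named. Even so, it leaves the list open to selection on observed imbalance.
- **Precision is not guaranteed to improve.** In the four-visit simulation the standard error rose slightly with covariate × time terms (0.0722 to 0.0732); with two visits it fell (0.0737 to 0.0717). Baseline TBR is the only covariate whose strength the documents support.

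**Conclusion.** The point holds in a limited form. For baseline covariates entered as main effects, which is the natural reading of the text, the adjusted between-arm difference in change is identical to the unadjusted one with complete data and nearly identical at the planned attrition. It neither corrects chance imbalance that predicts change nor gains precision. Only the group term, and with it the arm difference in level at a visit, responds.

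The invariance is algebraic and rests on no assumed values. The size of what is left uncorrected does: about 0.045 TBR units, a fifth of the detectable difference, for an assumed 0.5 SD imbalance and a slope of 0.1 per SD. Because the mixed model is additional to a valid primary t-test, this is a moderate correction to the analysis text and puts neither the primary conclusion nor the sample size in doubt.

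**What to change.** Replace the covariate sentence with wording to this effect:

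> The adjusted treatment effect will be estimated using two to four baseline covariates named before unblinding, with baseline values only. It will come either from the mixed model with each covariate entered together with its covariate × time terms, or from ANCOVA of the month-6 value on arm, the baseline value of the outcome and those covariates. That contrast will be reported as the adjusted effect, for TBR and for the secondary markers.

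Choose one of the two forms in advance. The gain to about 90% power in Step 6 comes from the ANCOVA form, because in the mixed model the baseline value is one of the responses. Delete the provision that lets covariates in because they differ between arms, and do not use values measured after randomization.

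The cost is wording and a few model terms. For markers measured at four visits, each covariate takes three further degrees of freedom for its time terms. For TBR it takes one, which is why the list should be short. The primary t-test and the sample size need no change.
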